Study Information

Title	Real-World Treatment Patterns and Outcomes in Postmenopausal, Hormone-Receptor Positive, Human Epidermal Growth Factor Receptor 2 Negative, Metastatic Breast Cancer Patients Treated with Palbociclib Plus an Letrozole as Initial Endocrine Therapy at Community Oncology Practices in the U.S.
Protocol number	A5481123
Protocol version identifier	1.0
Date	20 November 2018
Active substance	Palbociclib/PD332,991
Medicinal product	Palbociclib
Research question and objectives	
Objectives
 
Among postmenopausal women receiving palbociclib plus letrozole (palbociclib+LET) as initial endocrine therapy for hormone-receptor positive, human epidermal growth factor receptor 2 negative, advanced/metastatic breast cancer:
 
1. Describe the demographic and clinical characteristics of patients at the initiation of treatment.2. Describe the frequency of laboratory monitoring for hematologic and cardiovascular toxicities during treatment.3. Describe treatment patterns in terms of palbociclib+LET dosing, cycles received, and post-discontinuation treatment regimens.4. Describe clinical outcomes in terms of objective disease response rates and progression-free survival during treatment.

	CCI [REDACTED]
Author	[name] PPD Cardinal Health [name] Email: PPD Phone: PPD

TABLE OF CONTENTS

1. LIST OF ABBREVIATIONS	5
2. RESPONSIBLE PARTIES	6
3. ABSTRACT	7
4. AMENDMENTS AND UPDATES	10
5. MILESTONES	11
6. RATIONALE AND BACKGROUND	12
7. RESEARCH QUESTION AND OBJECTIVES	13
7.1. Objectives	13
CCI	
8. RESEARCH METHODS	15
8.1. Study Design	15
8.2. Setting	15
8.2.1. Inclusion Criteria	16
8.2.2. Exclusion Criteria	17
8.3. Variables	17
8.4. Data Sources	19
8.5. Study Size	19
8.6. Data Management	19
8.6.1. Case Report Forms (CRFs)/Electronic Data Record	20
8.6.2. Record Retention	20
8.7. Data Analysis	21
8.8. Quality Control	22
8.9. Limitations of the Research Methods	22
CCI	
9. PROTECTION OF HUMAN SUBJECTS	25
9.1. Patient Information	26
9.2. Patient Consent	26

9.3. Patient Withdrawal	26
9.4. Institutional Review Board (IRB)/Independent Ethics Committee (IEC)	26
9.5. Ethical Conduct of the Study	27
10. MANAGEMENT AND REPORTING OF ADVANCE EVENTS/ADVANCE REACTIONS	27
11. PLANS FOR DISSEMINATING AND COMMUNICATING STUDY RESULTS.....	28
12. REFERENCES	29
13. LIST OF TABLES	31
14. LIST OF FIGURES	31
15. ANNEX 1. LIST OF STAND ALONE DOCUMENTS	31
16. ANNEX 2. ADDITIONAL INFORMATION.....	31

1. LIST OF ABBREVIATIONS

Abbreviation	Definition
AE	Adverse event
AEM	Adverse event monitoring
AI	Aromatase inhibitor
CBC	Complete blood count
CBR	Clinical benefit rate
CR	Complete response
CRF	Case report form
DOT	Duration of treatment
ECOG-PS	Eastern Cooperative Oncology Group performance status
eCRF	Electronic case report form
EMR	Electronic medical record
ER	Estrogen receptor
HER2	Human epidermal growth factor receptor 2
HIPAA	Health Insurance Portability and Accountability Act
HR	Hormone receptor
HR	Hazard ratio
IRB	Institutional Review Board
ISPE	International Society for Pharmacoepidemiology
LET	Letrozole
MBC	Metastatic breast cancer
NE	Not evaluated
NIS	Non-interventional study
OPEN	Oncology Provider Extended Network
ORR	Objective response rate
PD	Progressive disease
PFS	Progression-free survival
PHI	Protected health information
PR	Partial response
PR	Progesterone receptor
RCT	Randomized controlled trial
SAP	Statistical analysis plan
SD	Stable disease

3. ABSTRACT

Title: Real-World Treatment Patterns and Outcomes Postmenopausal, Hormone-Receptor Positive (HR-positive), Human Epidermal Growth Factor Receptor 2 Negative (HER2-Negative), Metastatic Breast Cancer (MBC) Patients Treated with Palbociclib Plus Letrozole (Palbociclib+LET) as Initial Endocrine Therapy at Community Oncology Practices in the U.S.

Rationale and Background: Real-world research describing the demographic and clinical profile of patients, treatment patterns, and clinical benefit of palbociclib+LET as initial endocrine therapy for postmenopausal, HR-positive, HER2-negative MBC has been limited by small patient cohorts and short durations of follow-up. Similarly little is known regarding the profile of patients being prescribed newer agents such as ribociclib or what drives the continued use of aromatase inhibitor (AI) monotherapy as initial endocrine therapy for MBC with the availability of the cyclin-dependent kinase (CDK) 4/6 agents.

Research Question and Objectives: This study aims to describe demographics, clinical characteristics, toxicity monitoring, treatment patterns and clinical outcomes across a geographically diverse, representative cohort of MBC patients receiving palbociclib+LET according to its labeled indication at U.S. community oncology practices.

Objectives

Among postmenopausal women receiving palbociclib+LET as initial endocrine therapy for HR-positive, HER2-negative, MBC:

1. Describe demographic and clinical characteristics of patients at the initiation of treatment.
2. Describe the frequency of laboratory monitoring for hematologic and cardiovascular toxicities during treatment.
3. Describe treatment patterns in terms of palbociclib+LET dosing, cycles received, and post-discontinuation treatment regimens.
4. Describe clinical outcomes in terms of objective response rates (ORR), progression-free survival (PFS) during treatment and survival.

CCI

Study Design: This will be a retrospective, observational study with all data used having been collected as a routine part of clinical care. Providers will identify patients meeting the study selection criteria. Providers will be recruited to participate from the Cardinal Health Oncology Provider Extended Network, a community of over 7,000 clinical personnel treating cancer patients in the U.S. Providers who indicated treating patients of interest during a prior feasibility assessment will be asked to participate in the research. Providers will abstract data from his/her patients' medical records into an electronic case report form. Cardinal Health will conduct data verification via telephone and electronic follow-up with providers.

Population: The study will include adult female patients with HR-positive/HER2-negative MBC who were treated with palbociclib+LET as initial endocrine therapy on or after 03 February 2015. Providers will randomly select cases beginning with the earliest palbociclib+LET treated patient at least 3 months following the providers' first use of palbociclib.

CCI [REDACTED]

[REDACTED]

[REDACTED]

Variables: Patient demographics, clinical characteristics, treatments, complete blood count (CBC)/cardiac toxicity monitoring patterns, and clinical outcomes will be collected and analyzed.

Data Source: All data will be collected by the patients' treating physician and entered into the eCRF.

Study Size: This is a descriptive study and sample size calculation is not applicable. The target sample size of female, adult, HR-positive, HER2-negative MBC patients receiving initial endocrine therapy with palbociclib+LET is 200.

CCI [REDACTED]

[REDACTED]

Data Analysis: Descriptive analysis will be conducted to describe patient demographics, clinical characteristics, treatment and monitoring patterns, and clinical outcomes. For PFS and other time to event analyses, Kaplan-Meier methods will be used estimate the time to event accounting for right-censoring.

Milestones:

- Start of data collection: Q1 2019.
- Final study report: Q2 2019.

4. AMENDMENTS AND UPDATES

Amendment number	Date	Substantial or administrative amendment	Protocol section(s) changed	Summary of amendment(s)	Reason

5. MILESTONES

Milestone	Planned date
Project kickoff	30 May 2018
Study protocol development	Q3-Q4 2018
Study protocol finalization/approval	Q4 2018
Statistical analysis plan (SAP) & table shells	Q3-Q4 2018
SAP & table shells finalization/approval	Q4 2018
Case report form (CRF) development	Q4 2018
CRF finalization/approval	Q4 2018
Institutional review board preparation/submission/approval	Q4 2018
Electronic CRF (eCRF) programming & testing	Q4 2018
eCRF pre-test (n=4)	Q4 2018
Recruitment & data collection – Phase 1	Q1 2019
Interim report	Q1 2019
Recruitment & data collection – Phase 2	Q2 2019
Final results	Q2 2019
Final study report	Q2 2019

6. RATIONALE AND BACKGROUND

Palbociclib is approved for the treatment of HR-positive, HER2-negative MBC in combination with an AI as initial endocrine based therapy in postmenopausal women or in combination with fulvestrant in women with disease progression following endocrine therapy.¹ Approval was based on the randomized phase II PALOMA-1 trial, which demonstrated that the addition of palbociclib to letrozole significantly improved PFS in patients with advanced estrogen receptor positive (ER-positive)/HER2-negative MBC (median PFS, 20.2 months vs. 10.2 months; hazard ratio [HR]=0.448; $P=0.0004$).²

Palbociclib in combination with fulvestrant was approved one year later (February 2016) in pre- or postmenopausal women with disease progression following endocrine therapy based on results from the PALOMA-3 randomized controlled trial (RCT).³ In the phase III RCT, PALOMA-2, the findings of PALOMA-1 were confirmed. The median PFS estimate in the palbociclib+LET arm was 24.8 months compared to 14.5 months in the placebo plus letrozole arm (HR=0.58; $P<0.001$).⁴

Since the initial approval of palbociclib in February 2015, real-world observational studies have described treatment patterns, dose modifications, and tolerability using multiple distinct retrospective databases.⁵⁻⁸ Estimates of the clinical benefit (partial response or better as reported by the treating provider) of palbociclib+LET presented in early 2018 were markedly similar ranging from 79.5% to 83.5%.^{6,8} Landmark PFS analysis varied between the two studies ranging from 80.0% to 96.7% at 6 months, 67.1% to 84.1% at 12 months, and 54.7% to 69.3% at 18 months.^{6,8} A 24-month estimate was available from one study (reported the higher estimates at each of the 6-, 12-, and 18-month interval previously referenced), which found 64.3% of patients were progression-free at 24 months. With an additional year of real-world experience accrued since the time of data collection for these studies, more precise estimates of disease response and PFS are available.

The prior research was not statistically powered to compare outcomes between palbociclib-treated patients to those who received LET monotherapy. A large proportion of female HR-positive/HER2-negative MBC continue to be prescribed AI monotherapy in lieu of the results of the PALOMA trials.⁹ Moreover, recently published research indicates a higher rate of discontinuation (45.8% vs. 34.5%) for women prescribed AI-monotherapy.⁹ The differences in the demographic and clinical disease characteristics of women receiving first-line treatment with LET versus those prescribed palbociclib+LET have not been explored nor have clinical outcomes between them been compared. Additionally, since the completion of the previously described real-world research ribociclib was approved in same indication as palbociclib in March of 2017 (in combination with an AI as initial endocrine-based therapy for the treatment of postmenopausal women with HR-positive/HER2-negative MBC).¹⁰ No real-world data on clinical characteristics, treatment patterns (including dose reductions and rates of discontinuation), or early estimates of rates of progression have been explored in a real-world cohort of ribociclib+AI treated patients. Further exploration of treatment patterns and clinical outcomes in terms of rates of progression, which patients receive LET or ribociclib+AI, and the outcomes of this treatment is needed to understand the types of patients most likely to benefit from palbociclib+LET in the indicated population.

7. RESEARCH QUESTION AND OBJECTIVES

The main objective of this study is to describe patient demographics, clinical characteristics, toxicity monitoring, treatment patterns and clinical outcomes among postmenopausal, female, HR-positive, HER2-negative, MBC patients receiving palbociclib+LET as initial endocrine therapy. Demographic and clinical characteristics and outcomes will be presented overall, and among groups for the following three planned primary grouping variables:

1. Visceral vs. non-visceral at the initiation of initial endocrine therapy for MBC.
2. Received prior neo/adjuvant endocrine therapy versus no prior neo/adjuvant therapy.
3. De novo metastatic disease versus ≤ 12 months disease free interval since prior neo/adjuvant treatment versus > 12 months disease free interval since prior neo/adjuvant treatment.

[figure not shown]
7.1. Objectives

Among MBC patients receiving palbociclib+LET according to its labeled indication as initial endocrine therapy for MBC the research objectives are to:

1. Describe the demographic and clinical characteristics of patients at the initiation of treatment:
 - a. Demographic characteristics will include age, race/ethnicity, body mass index, insurance status, state of residence at the date of MBC diagnosis and palbociclib initiation. Employment status will be assessed to the extent documented in the record. Overall duration of follow-up (months) from the initiation of palbociclib+LET will be presented.
 - b. Clinical characteristics will include year of breast cancer and MBC diagnosis, stage of initial diagnosis, menopausal status, number and sites of distant metastasis at MBC diagnosis and palbociclib initiation, verification of HER2 and ER/progesterone receptor (PR) status, histology, menopausal status at palbociclib+LET initiation, performance status and comorbid disease burden, including cardiovascular-related comorbidities (at MBC diagnosis and at palbociclib initiation), and modalities of treatment received in the neoadjuvant or adjuvant setting (chemotherapy, hormone therapy, surgery, radiation therapy).
2. Describe the frequency of laboratory monitoring for hematologic and cardiovascular toxicities during treatment:
 - a. Note that CBC monitoring and cardiac function monitoring will be assessed, but lab results/values will not be assessed under this objective.

- b. Evaluate the extent of laboratory monitoring using CBC per cycle:
 - i. The frequency of assessment of CBC with or without differential will be evaluated during the initial endocrine-based therapy for MBC.
 - c. Assess the frequency of cardiac toxicity monitoring using electrocardiogram, liver function panels, and electrolytes:
 - i. The frequency of assessment of cardiac monitoring by each method will be evaluated during the initial endocrine-based therapy for MBC.
3. Describe treatment patterns in terms of palbociclib+LET dosing, cycles received, and post-discontinuation treatment regimens:
 - a. Palbociclib dosing will include description of the starting dose, dose adjustment, discontinuation, and time to dose adjustment for palbociclib.
 - b. Duration of palbociclib in terms of the number of cycles completed prior to the discontinuation of initial treatment for MBC.
 - c. Treatment patterns includes the distribution of regimens administered, by line, from MBC diagnosis through the end of the medical record.
 - d. Treatment patterns also includes the sequence of treatments across lines, from MBC diagnosis through the end of the medical record.
4. Describe clinical outcomes in terms of objective disease response rates and progression-free survival during treatment:
 - a. Describe the rate of objective disease response during initial endocrine-based therapy:
 - i. Tumor response will be classified per provider report for each regimen received during MBC treatment.
 - ii. Tumor response will be classified under a primary response classification as complete response (CR), partial response (PR), stable disease (SD), progressive disease (PD), and unknown/not evaluated (NE).
 - iii. Tumor response will be classified under a secondary response classification as matching the primary classification, but patients with NE responses classifiable as Other Favorable or Other Unfavorable so classified.
 - b. Describe progression-free survival and/or time to progression from the initiation of initial endocrine-based therapy:
 - i. Landmark PFS and/or rate of progression at 3, 6, 12, 18, and 24 months.
 - ii. Proportion alive at 6, 12 and 24 months.

CCI

8. RESEARCH METHODS

8.1. Study Design

The current study will be conducted as a retrospective observational cohort study using a chart review methodology. Providers in the Cardinal Health Oncology Provider Extended Network (OPEN) will be recruited to participate in the patient identification and data abstraction for this research study. All study data are secondary data and will have been collected retrospectively from existing clinical data originally collected as part of routine care.

Patient eligibility will be confirmed by the treating physician. Providers will abstract the patient level data necessary to achieve the research objectives into an electronic case report form (eCRF). Providers may complete a maximum of 20 eCRFs; verification of submitted data will be performed by Cardinal Health Clinical Research Operations via clinical data quality review of submitted eCRFs (further description of data verification processes are provided in [Section 8.8](#)). In order to achieve the research objectives related to the estimation of a 24-month PFS, providers will be asked to select consecutive patients starting with the earliest patient treated with palbociclib+LET meeting all the study eligibility requirements (See [Section 7.2](#)). In addition, providers will be asked to consider the “earliest” palbociclib+LET treated patient as the first patient treated 60 days after the first instance they prescribed palbociclib+LET in clinical practice outside of a clinical trial. In total up to 200 patients treated with palbociclib+LET per labeled indication will be identified.

8.2. Setting

Providers from OPEN will identify patients meeting the study selection criteria. OPEN is a community of over 7,000 oncologists, hematologists and urologists providing care to cancer patients geographically distributed across the U.S. and practicing in both community and academic research settings. OPEN community members include medical doctors, nurse practitioners, pharmacists and other individuals providing care to cancer patients.

Community members are not limited to any specific group purchasing organization or any other membership requirements. Community members are included in OPEN if they and their practice utilizes Cardinal Health’s proprietary Point-of-Care claims remittance software for practice management purposes or if they have participated in Cardinal Health sponsored research activities. Providers within the OPEN database are evenly distributed between regions (Northeast, Midwest, South and West regions) across different size practices (small, medium or large practice) and years of experience in providing cancer care.

To be eligible for participation in this research study, a physician must have treated or be treating two or more HR-positive/HER2-negative MBC patients who meet the eligibility criteria for the study. Providers who responded to the initial feasibility survey will be the first set of physicians asked to participate in the research. Should further recruitment be required to achieve the desired sample size Cardinal Health will recruit from its entire database of providers.

Providers will be allowed to complete up to 20 eCRFs. Providers will be asked to indicate the number of patients considered eligible for the research but for whom records were not entered. No data for the patients not entered into the eCRF will be collected. Providers must also be able to participate in the research monitored by a central Institutional Review Board (IRB). No site specific IRB approval will be sought and providers requiring this approval will not be eligible.

After IRB approval of the research protocol, the eCRF will be pre-tested with 4 providers; data collected as part of the pre-test will not be used in the final analytical dataset. After testing and revisions (if necessary), providers who completed a feasibility assessment for the research will be contacted and asked to participate in the research. Data collection will be conducted over the course of 4-weeks. Providers are compensated at fair market value for each completed and verified eCRF assuming a rate of payment based on one hour of data collection (see [Section 8.6.1](#)).

8.2.1. Inclusion Criteria

Patients must meet all of the following inclusion criteria to be eligible for inclusion in the study:

1. Diagnosed with locoregional recurrent or metastatic female breast cancer.
2. Pathologically confirmed HR-positive/HER2-negative diagnosis.
3. Received treatment with palbociclib in combination with letrozole as initial endocrine-based therapy for advanced/metastatic breast cancer:
 - a. Initiated treatment with palbociclib at least 3 months following the provider's first use of palbociclib following its FDA approval.
 - b. At least 1 month of follow-up (at least one visit with the provider) after initiation of palbociclib.
4. Postmenopausal (or receiving surgical or medical treatment to induce menopause) at the time of initiation of palbociclib.
5. ≥ 18 year old at initiation of palbociclib.

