2.1 STUDY POPULATION

CCI

[REDACTED]

- 1) Patients treated with palbociclib+LET as initial endocrine therapy for MBC per the palbociclib U.S. FDA approval label;

CCI

[REDACTED]

The target sample size for each of the three cohorts is 200 patients. Table 1 illustrates the selection criteria for each of the cohorts. Patients must meet all of the following inclusion criteria to be eligible for inclusion in the study. No exclusion criteria will be imposed for the selection of patients.

Table 1. Cohort Selection Criteria.

Palbociclib+LET	CCI
Diagnosed with locoregional recurrent or metastatic female breast cancer	
Pathologically confirmed HR-positive/HER2-negative tumor	
Received treatment with palbociclib in combination with LET as initial endocrine-based therapy for advanced/metastatic breast cancer 
 - Initiated treatment with palbociclib at least 3 months following the provider's first use of palbociclib after 03 Feb 2015 - At least 1 month of follow-up data after initiation of palbociclib 	
Postmenopausal (or receiving surgical or medical treatment to induce menopause) at the time of initiation of 1L treatment for locoregional recurrent or BMC	
≥18 year old at initiation of endocrine therapy	

Patient eligibility will be confirmed by the treating physician. Providers may complete a maximum of 20 eCRFs. Providers will be asked to randomly select patients from the pool of eligible patients and verify that they have performed random patient selection.

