- d. Treatment patterns includes the distribution of regimens administered, by line, from MBC diagnosis through the end of the medical record
- e. Treatment patterns also includes the sequence of treatments across lines, from MBC diagnosis through the end of the medical record

4) Describe the rate of objective disease response during initial endocrine-based therapy

- a. Tumor response will be classified per provider report for each regimen received during MBC treatment
- b. Tumor response will be classified under a primary response classification as complete response (CR), partial response (PR), stable disease (SD), progressive

disease (PD), and not evaluable (NE), and unknown which comprises any other status

- c. Tumor response will be classified under a secondary response classification as matching the primary classification, but for patients with NE, responses classifiable as “Other Favorable” or “Other Unfavorable”

5) Describe PFS from the initiation of initial endocrine-based therapy

- a. Proportion of patients who are persistent to initial endocrine-based therapy for MBC at 3, 6, 12, 18, and 24 months, with persistence defined as the duration of initial regimen until one of the following events occurs: a regimen change or switch, treatment discontinuation, disease progression, or death.
- b. Landmark PFS at 3, 6, 12, 18, and 24 months
- c. Proportion alive at 3, 6, 12, 18 and 24 months

CCI

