7.2 SURVIVAL ANALYSIS

[figure not shown]
Survival analysis, also called time to event analysis, will be used in the current research to estimate the time to treatment discontinuation, time to progression, and PFS in 1L. This method of analysis is employed when non-informative right-censoring occurs as is the case for this study since not all patients will have discontinued treatment, progressed or died by the end of the study period. The Kaplan-Meier method (product limit estimator) will be used to generate median estimates of time to progression and PFS if median time is reached within the population. Survival curves will also be generated. In addition to calculating the median survival estimate, the life-table method will be used to estimate these time to event outcomes at successive 3 month intervals through 24 months post initiation of 1L.

The following lists the measurements to be conducted using survival analysis techniques:

1. Median time to treatment discontinuation
 - a. Proportion of patients (survival estimate and 95% confidence interval) who are still receiving 1L treatment at 3, 6, 12, 18, and 24 months post 1L initiation
 - b. Event = any treatment discontinuation for any reason, censor = patients who are still on 1L therapy at data cut-off
2. Median time to progression
 - a. Proportion of patients (survival estimate and 95% confidence interval) who are progression free at 3, 6, 12, 18, and 24 months
 - b. Event = any treatment discontinuation for disease progression, censor = patients who are still on 1L therapy or who discontinued therapy for any reason other than disease progression at data cut-off
3. Median progression-free survival
 - a. Proportion of patients (survival estimate and 95% confidence interval) who are progression free and alive at 3, 6, 12, 18, and 24 months

- b. Event = any treatment discontinuation for disease progression or death, censor = patients who are still on 1L therapy or who discontinued therapy for any reason other than disease progression or death at data cut-off
- 4. Proportion of patients alive at 3, 6, 12, 18, and 24 months following 1L initiation
 - a. Event = death, censor = date of last follow-up among patients who are not deceased

CC
I

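### Requiring one month of observed follow-up while the survival and PFS clocks start at initiation shuts out first-month deaths and biases those landmarks slightly upward

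*Protocol*

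**What the plan says.** Eligibility: Protocol 8.2.1 item 3b requires "At least 1 month of follow-up (at least one visit with the provider) after initiation of palbociclib". SAP 2.1, Table 1, words it as "At least 1 month of follow-up data after initiation of palbociclib". Both describe follow-up that took place, not calendar time that was available.

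Time origin: SAP 2.4 sets out to "Describe PFS from the initiation of initial endocrine-based therapy" and lists "Landmark PFS at 3, 6, 12, 18, and 24 months". SAP 7.2 item 4 reports "Proportion of patients alive at 3, 6, 12, 18, and 24 months following 1L initiation".

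Events in SAP 7.2:
- PFS: "Event = any treatment discontinuation for disease progression or death".
- Survival: "Event = death, censor = date of last follow-up among patients who are not deceased".
- Time to progression: "Event = any treatment discontinuation for disease progression, censor = patients who are still on 1L therapy". Death is not an event here.
- Time to discontinuation: stopping for any reason. SAP 7.1 lists death among the reasons.

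No readable text provides for delayed entry, a conditional label on the landmarks, or a sensitivity analysis for the one-month rule. The readable limitations in Protocol 8.9 do not mention it.

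**The concern.** Entry depends on something that happens after time zero. A patient who dies in week 2 has less than a month of follow-up and is ineligible, yet the patients who do enter are treated as if they could have died from day 0. The survival and PFS landmarks then describe patients who lived and were followed for a month, while their labels say from initiation.

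The planned safeguard cannot show this. Protocol 8.2 and 8.9 gauge patient selection by comparing the number of eligible patients with the number submitted. Patients who fail 3b are not eligible, so they appear in neither count, and no data are collected on patients who are not entered. The size of the effect therefore could not be recovered afterwards.

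What is at stake is the accuracy of the PFS and survival landmarks, which are main descriptive outputs of the study.

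**Working it through.** The plan states no figure on this point, so there is none to reproduce.

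**Inputs.** From Protocol 6: a 6-month real-world PFS of 80.0% (the lower of two studies), 6-month and 24-month PFS of 96.7% and 64.3% (the higher study), and a trial median PFS of 24.8 months. From Protocol 8.5: n=200. Assumed: one-month mortality q of 0.25% to 2%, and a survival landmark of 90% for illustration.

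**Inflation factor.** Being event-free beyond t ≥ 1 month implies being alive at 1 month. Selecting on survival to 1 month therefore gives
- survival: P(OS > t | OS > 1) = OS(t)/OS(1)
- PFS: P(PFS > t | OS > 1) = PFS(t)/OS(1)

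with OS(1) = 1 − q. The overstatement is S(t)/(1 − q) − S(t). For example, 80.0/0.98 − 80.0 = 1.63 points.

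| True landmark | q = 0.25% | 0.5% | 1% | 2% |
|---|---|---|---|---|
| 6-month PFS 80.0% | 0.20 | 0.40 | 0.81 | 1.63 |
| 24-month PFS 64.3% | 0.16 | 0.32 | 0.65 | 1.31 |
| Survival 90% (illustrative) | 0.23 | 0.45 | 0.91 | 1.84 |

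(Percentage points. Early losses are taken as neutral.)

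**Check on the range of q.** OS(1) cannot be below PFS(1). In the lower study, a constant hazard gives PFS(1) = 0.80^(1/6) = 0.9635, so q up to 2% is possible. In the higher study, PFS(1) = 0.967^(1/6) = 0.9944, so under a constant hazard q could not exceed 0.56%, and the bias at 64.3% would be at most 64.3/0.9944 − 64.3 ≈ 0.36 points. The 1% and 2% columns of that row need a hazard that is higher early on.

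**Precision at n=200, ignoring censoring.** Half-width = 1.96 × √(p(1 − p)/200):
- p = 0.800: 1.96 × √(0.16/200) = 5.5 points
- p = 0.643: 1.96 × √(0.2296/200) = 6.6 points

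**Month 1 still contains PFS events.** Take time to progression as exponential with median 24.8 months, and q = 1% independent of progression. The probability of no progression in month 1 is 0.5^(1/24.8) = 0.9724. Without selection, the probability of a first-month PFS event is 1 − 0.9724 × 0.99 = 3.7%. Among included patients it is 1 − 0.9724 = 2.8%. Only the deaths disappear.

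**Other endpoints.** Time to discontinuation loses only patients who die or are lost in month 1; someone who stops early and is still seen later is eligible and counted. Time to progression has no death event, so it is not inflated by this route if early death is independent of progression.

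**The case against.** A reader might infer that the first month is free of every PFS event, so that the factor is 1/PFS(1). Under a constant hazard, that would move a 6-month PFS of 80.0% to 80.0/0.9635 = 83.0%. The documents do not support this. Item 3b asks for follow-up and a visit, not for being progression-free or still on treatment. A patient who progresses in week 3 and is seen in week 5 is eligible and counts as a PFS event. The 83.0% would need every first-month progressor also to die or be lost within that month.

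Two other strong readings fail. Not every landmark is inflated, because time to progression need not be. Nor is the net direction of the whole rule known, because 3b also removes early losses, whose effect could go either way; the upward direction is established for the excluded deaths.

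It can also be said that the effect is small against sampling error, and that no readable analysis formally compares the results with the trial or earlier real-world rates quoted as background. Both statements are true. They lower the priority but do not remove the defect: the bias does not shrink with more patients.

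A lenient provider might take the bracketed visit as the whole test and admit some early deaths. The SAP wording, which asks for a month of data, points the other way. Text after Protocol 8.9 and between SAP 7.2 and 7.4 is redacted, so handling there cannot be ruled out.

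**Conclusion.** The point holds in limited form. As written, the plan excludes first-month deaths while labelling survival and PFS as measured from initiation, and both sets of landmarks are overstated by 1/OS(1). For one-month mortality of 0.25% to 2%, that is about 0.2 to 1.6 points on a 6-month PFS of 80.0% and 0.2 to 1.3 points on a 24-month PFS of 64.3%. The mortality range is an assumption, and early losses are treated as neutral. The effect is probably small beside the sampling error, but it is systematic, invisible to the planned selection check and cheap to avoid.

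**What to change.** Reword Protocol 8.2.1 item 3b and SAP Table 1 to potential follow-up: palbociclib+LET was started at least 1 month before the abstraction date, whatever happened afterwards. Drop the requirement for a later visit, since it would bring the same exclusion back. Early deaths then enter as events, and patients lost early are censored at last contact. The cost is one sentence in each document, a few very short records and slightly lower landmarks.

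If 3b has to stay:
- keep the clock at initiation;
- label the survival and PFS landmarks as conditional on being alive and followed at 1 month;
- ask each provider how many patients 3b excluded and how many of them died, so that OS(1) can be bounded.

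Do not restart the clock at month 1. It recovers no deaths and leaves the Kaplan-Meier survival values unchanged. For PFS it would discard first-month progressions that are now counted, moving the estimate towards the 83.0% figure above and further from PFS measured from initiation.
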